Inherited bone marrow failure syndromes are genetic disorders that may present at birth or later in life and are characterized by defective single or multi-lineage hematopoiesis with many patients progressing to develop severe aplastic anemia (SAA) and they are often associated with congenital defects. Patients are at risk for significant infections due to neutropenia; however many patients also have an additional underlying immunodeficiency. In addition, patients with bone marrow failure syndromes are at particularly increased risk for developing malignancies; in particular myelodysplastic syndrome (MDS), acute myeloid leukemia, and solid tumors. For those patients who develop SAA, the primary curative therapy is hematopoietic cell transplantation (HCT). In addition, although not the primary goal for patients with bone marrow failure associated SAA, HCT has been used to try and prevent the development of MDS and myeloid leukemias.

a. Dyskeratosis congenita

Dyskeratosis congenita (DC) is a rare inherited multi-system disorder characterized by the diagnostic triad of reticulated hyperpigmentation of the skin, dystrophic nails, and oral leukoplakia. In addition, several somatic manifestations are seen including skeletal, dental, gastrointestinal, genitourinary, pulmonary, immunological and ocular abnormalities.³⁸ Autosomal dominant and recessive forms have been described; however over 75% of the cases are an X-linked recessive pattern. The genes identified have been found to encode products involved in telomere maintenance. The primary causes of death are from bone marrow failure culminating in SAA. A recent analysis of data from the dyskeratosis congenita registry found the probability of developing bone marrow failure [one or more

peripheral cytopenia(s)] by age 40 to be around 94%.³⁸ In addition to death from infections as a result of bone marrow hypoplasia, a large number of patients die from infections resulting from cellular and humoral abnormalities of the immune system. Specifically, studies have found abnormal immunoglobulin production, reduced B and or T lymphocyte numbers and reduced T-cell function in patients with DC.³⁹ Other causes of death include myeloid and solid tumor malignancies as well as pulmonary failure.

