| Regimen B: For patients receiving unrelated umbilical cord blood | | |
|---|---|--|
| Day | Treatment | Dose |
| -6 | Treosulfan | 14 grams/m ² /day IV ^a |
| | Treosulfan PK sampling ^b | |
| | Fludarabine | 30 mg/m ² /day IV ^a |
| -5 | Treosulfan | 14 grams/m ² /day IV ^a |
| | Treosulfan PK sampling ^c | |
| | Fludarabine | 30 mg/m ² /day IV ^a |
| -4 | Treosulfan | 14 grams/m ² /day IV ^a |
| | Fludarabine | 30 mg/m ² /day IV ^a |
| | Rabbit Antithymocyte globulin (ATG; Thymoglobulin®) | 1.0 mg/kg/day IV ^d |
| -3 | Fludarabine | 30 mg/m ² /day IV ^a |
| | Rabbit Antithymocyte globulin (ATG; Thymoglobulin®) | 2.5 mg/kg/day IV ^d |
| -2 | Fludarabine | 30 mg/m ² /day IV ^a |
| | Rabbit Antithymocyte globulin (ATG; Thymoglobulin®) | 2.5 mg/kg/day IV ^d |
| -1 | Recipients with underlying T-cell primary | TBI 200 cGy |
| | Immunodeficiency or | |
| | All other recipients | TBI 300 cGy |
| 0 | Unrelated umbilical cord blood infusion | |

^a For patients >120% ideal body weight (IBW) BSA will be calculated using adjusted weight

^b Research Treosulfan PK sampling (7 timepoints): All patients, see **section 14B.7** for details

^c Research Treosulfan PK sampling (7 timepoints): Only in patients who are < 4 years of age at time of start of conditioning, see **section 14B.7** for details.

^d Actual body weight

Conditioning regimen.**The regimen will consist of:****1. Treosulfan.**

Treosulfan will be administered intravenously over 120 minutes for three consecutive days (day -6 to -4). Use actual weight to calculate BSA. For patients >120% of ideal weight, use adjusted weight to calculate BSA. Optional pharmacokinetic evaluation will be performed on days -6 (all patients) and -5 (only in patients who are < 4 years of age at time of start of conditioning; see Section 14B.7).

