Patients with an underlying T-cell immunodeficiency will receive 200 cGy TBI on day -1. All other patients will receive 300cGY TBI on day – 1. See institutional standard practice guidelines for radiation (**Appendix B**).

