19. STATISTICAL CONSIDERATIONS AND TERMINATION OF STUDY

The primary objective of this clinical trial is to evaluate, within the limits of a phase II study, the preliminary efficacy as defined by engraftment, of a regimen consisting of treosulfan and fludarabine followed by allogeneic HCT in patients with nonmalignant inherited disorders. We plan to enroll at least 30 patients on this study. A minimum of 30 patients will be enrolled onto Arm A. The protocol will continue to accrue until this goal is met. There will be no set limit for Arm B: the cord blood arm. Analyses will be carried out separately between Arm A and B. We will be encouraged to continue study of this treatment if at least 27 of 30 patients engraft. Table 5 shows the probability of observing 27 or more successes among 30 patients for several possible true rates of engraftment.

The protocol was modified in January 2011 and September 2011. Due to a higher than anticipated incidence of acute grade III-IV GVHD for both arms in the first 13 patients (5/13 = 38%; 3/8 bone marrow recipients, 2/5 cord blood recipients) the protocol was modified to add rabbit ATG (thymoglobulin) to both arms initially for unrelated recipients (January 2011) and subsequently for the related recipients (September 2011). In addition, due to graft rejection (n=1) and low donor chimerism/inadequate disease response (n=1) in 2 of the 5 patients enrolled onto the cord blood arm, the cord blood arm was modified to increase the TBI from 200 cGy to 300 cGy TBI for non T-cell deficient patients. The revised protocol will reset the target accrual to at least 30 patients as of January 2011, with a minimum enrollment of 30 onto Regimen A (as stated above). The efficacy analysis will be performed separately for the initial 13 patients (Regimen A: n=8, Regimen B: n=5) and those accrued under the modified regimen. Only patients enrolled after this protocol modification will be counted towards the stopping rules.

Table 5. Probability of observing 27 or more successes in 30 patients

| True rate of engraftment | Pr(\geq 27 successes) |
|--------------------------|--------------------------|
| 70% | 0.01 |
| 80% | 0.12 |
| 90% | 0.65 |
| 95% | 0.94 |

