200 cGy TBI (for unrelated cord blood recipients with an underlying T-cell primary immunodeficiency)
OR
 300 cGy TBI (for all other unrelated cord blood recipients)

Signature of **Local** Principal Investigator: _____ Date: _____
 (or Designee)

Transplant Center _____

Signature of **FHCRC** Principal Investigator _____ Date: _____
 (or Designee)

Signature of person completing form: _____ Date: _____

FHCRC Patients:

Signature of Principal Investigator: _____ Date: _____
 (or Designee)

OR

Outside Center Patients:

Signature of **Local** Principal Investigator: _____ Date: _____
 (or Designee)

Signature of **FHCRC** Principal Investigator: _____ Date: _____
 (or Designee)

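### The Section 9 treatment text gives the lower Regimen B TBI dose for any underlying T-cell immunodeficiency, while the Section 9 table and Appendix F limit it to a primary one

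*Combined protocol and SAP*

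**What the plan says.** Four places tie the Regimen B TBI dose to T-cell status.

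- **Section 9, Regimen B conditioning table, day -1.** The 200 cGy row begins "Recipients with underlying T-cell primary" and continues on the next line with the word immunodeficiency. The 300 cGy row is for "All other recipients".
- **Section 9, item 4 (Total Body Irradiation).** "Patients with an underlying T-cell immunodeficiency will receive 200 cGy TBI on day -1", and then "All other patients will receive 300cGY TBI on day" -1. The word *primary* is absent.
- **Appendix F, TBI Dose Assignment.** One of two boxes must be marked for each Regimen B patient. The first reads "200 cGy TBI (for unrelated cord blood recipients with an underlying T-cell primary immunodeficiency"; the second gives 300 cGy to all remaining unrelated cord recipients.
- **Section 19.** The account of the 2011 modification says the change was to "increase the TBI from 200 cGy to 300 cGy TBI for non T-cell deficient patients".

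The background section describes patients who could be caught between these wordings. Section 3A, item 6a, reports "reduced B and or T lymphocyte numbers and reduced T-cell function in patients with DC" (dyskeratosis congenita).

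**The concern.** The table and the treatment text are both dosing instructions, stand in the same section, and do not describe the same group. *T-cell immunodeficiency* is wider than *T-cell primary immunodeficiency* if a patient can have an underlying T-cell deficit as part of a disease that the protocol does not class as a primary immunodeficiency. For such a patient the two instructions give different radiation doses.

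At stake is a clear, single conditioning instruction in a multicenter trial. Section 19 says that the TBI dose was changed after one graft rejection and one case of low donor chimerism with inadequate disease response among the first 5 cord recipients, so the investigators themselves treated the choice of dose as important. Section 19 also sets no accrual limit for the cord arm, so further patients may be assigned under whichever wording is read.

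**Working it through.** There is no figure in the plan to reproduce. The check is a comparison of texts.

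**Step 1: find every statement of the rule.** Besides the four places above, Section 15D names both doses but gives no criterion.

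**Step 2: set the criteria side by side.**

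| Place | Status | 200 cGy | 300 cGy |
|---|---|---|---|
| Section 9 table | Instruction | T-cell primary immunodeficiency | All others |
| Appendix F | Instruction (registration form) | T-cell primary immunodeficiency | All others |
| Section 9, item 4 | Instruction | T-cell immunodeficiency | All others |
| Section 19 | Account of a past change | By implication, any T-cell deficient patient | Those not T-cell deficient |

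The table and the form agree. Section 19 matches the wider wording in effect, but it is history and nobody doses from it. That leaves two operative rules: item 4 against the table and the form. They differ by one word.

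**Step 3: apply both rules to three kinds of cord recipient.**

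| Recipient | Table and Appendix F | Item 4 |
|---|---|---|
| T-cell primary immunodeficiency | 200 cGy | 200 cGy |
| No T-cell deficiency | 300 cGy | 300 cGy |
| T-cell deficiency within a marrow failure syndrome | 300 cGy, if *primary* excludes marrow failure | 200 cGy |

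Only the third row conflicts. The gap is 300 − 200 = 100 cGy, and 100/200 = 50% above the lower dose.

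**Step 4: does the third row describe a real kind of patient?** Section 3A, item 6, says that many patients with inherited marrow failure also have an immunodeficiency, and item 6a reports lower T-cell numbers and function in dyskeratosis congenita. Item 6b mentions T-cell abnormalities in Shwachman-Diamond syndrome, a weaker example because it does not call them a T-cell immunodeficiency. Both diseases are eligible as inherited marrow failure syndromes.

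**Step 5: does *primary* exclude marrow failure?** The staging tables in Section 14 have one table for primary immunodeficiency and another for marrow failure, with dyskeratosis congenita in the second. The October/November 2015 paragraph of Section 19 also lists the two as separate subgroups. This supports the reading but does not define the term for Regimen B.

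**Step 6: does anything else settle it?** No diagnosis list, cell count or function threshold is attached to any of the terms. The primary immunodeficiency table names several diseases without marking which count as T-cell disorders. That table recommends lymphocyte subsets and function tests before transplant (with exceptions for some diseases), but the marrow failure table lists neither. Under the wider rule, the disputed group therefore has no recommended test that would establish T-cell status.

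**The case against.** The strongest defense is that item 4 is shorthand for the group in the table, and that the dose is in practice fixed elsewhere. Section 8B makes the Appendix F form part of registration at collaborating institutions. The form requires one dose to be marked, uses the narrower wording, and for outside-center patients carries signature lines for both the local and the coordinating-center principal investigator. The disease groupings in Section 14 organize recommended tests, and the 2015 list is given by way of example for Regimen A accrual, so neither was written as a dosing taxonomy for Regimen B.

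Much of this stands. The form is a real control and makes site-by-site divergence less likely. But it does not remove the conflict: a correctly completed form can contradict the treatment text that the same center follows, and no passage says which governs. The shorthand reading is possible but unstated, and the background text on marrow failure leaves room for the wider one.

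Several stronger readings are tempting and are not supported:

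- *Four different criteria.* There are two operative rules, as the table in Step 2 shows.
- *A link to the Regimen B deaths.* Section 19 reports 3 deaths among 5 patients enrolled after the January 2011 changes, but says their causes could not be tied to one component of the regimen.
- *A share of the arm*, such as one patient in 10 to 15. A denominator of 15 would include the first 5 cord recipients, who preceded the 200/300 split, are analyzed separately and do not count toward the stopping rules. The arm also has no fixed size.
- *Corrupted stopping-rule counts.* Regimen B pools both doses by design, and its limits are not split by dose.
- *Extension to HLH.* The documents do not describe T-cell deficiency in that disease.

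**Conclusion.** The plan is inconsistent as written, in a narrow but operative way. Section 9, item 4, assigns 200 cGy by a wider criterion than the Section 9 table and Appendix F. For a T-cell deficient cord recipient with a marrow failure syndrome, a literal reading gives doses 100 cGy apart.

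The conclusion that this patient falls on different sides rests on one assumption, that *primary* excludes marrow failure syndromes. The mismatch in wording and the lack of any definition do not depend on it.

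The practical size is unknown. The documents report no cord recipient of this kind, so the number affected may be zero. A reader might infer that patients with the same disease are already being conditioned differently at different sites. The documents do not show this, and the Appendix F designation makes it less likely. The point is a contradiction in a radiation-dose instruction that is worth removing, and makes no claim that any outcome was affected.

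**What to change.** Reconcile Section 9, item 4, with the Regimen B conditioning table and Appendix F so that all three state one criterion, and bring the description in Section 19 into line with it. The investigators should choose that criterion and define it, for example by a list of diagnoses or a stated laboratory definition, so that a T-cell deficient patient with a marrow failure syndrome falls clearly on one side at registration. If the definition relies on a laboratory result, the test should also appear in the pre-transplant evaluation for the marrow failure group. This review does not say which criterion or dose is right.

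The cost is a wording amendment and a check of the form, with no added patients. A test is added only if the investigators choose a laboratory definition.

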10. COLLECTION OF HEMATOPOIETIC STEM CELLS/INFUSION

Related donors will be collected at each participating center and unrelated donors will be collected through the NMDP or other donor collection centers.

- A. PBSC:** Is the preferred stem cell source for fully matched donors. PBSC may also be used for a mismatched donor following discussion with the PI. PBSC collection and infusion will be according to institutional standard practice guidelines.
- B. Bone Marrow:** Donors will undergo standard bone marrow harvest following each center's standard practice. The marrow will be infused according to each center's standard practice guidelines.
- C. Unrelated Umbilical Cord Blood: will be used if an HLA-matched related or unrelated donor is not identified or available (see matching criteria section 6)**
 - 1. Procedures for requesting, receiving and characterizing the cord blood unit for infusion will be according to institutional standard practice.
 - 2. Pre-infusion hydration should be performed per institutional guidelines.
 - 3. For FHCRC patients, the cord blood unit should be thawed and infused per FHCRC standard practice guidelines. Cord blood products should be infused without delay as soon as the product arrives on the unit.
 - 4. The infusion should take no longer than 30 minutes per unit. Pre-medications prior to cord blood infusion will be per institutional standard practice guidelines. Under no circumstances is the cord blood to be irradiated. No medications or fluids should be given piggyback through the catheter lumen that is being used for cord blood infusion.
 - 5. The product is infused via IV drip directly into the central line according to standard practice with gravity filtered tubing.
 - 6. Vital signs should be monitored before beginning the infusion and periodically during administration. Notify the attending physician, fellow, PA, or NP immediately if the patient exhibits signs or symptoms of a reaction.
 - 7. Benadryl, epinephrine, and hydrocortisone should be available at the bedside for emergency use if necessary. Oxygen with nasal prongs for standby use should be present in the room.
 - 8. If the patient is a double cord blood recipient, the two units may be given consecutively with no wait between infusions of the units. The start and stop time of each unit should be recorded on the infusion record.
- D. Combined bone marrow and cord blood from the same HLA-matched sibling donor:** At the discretion of the PI, bone marrow and cord blood cells from the same HLA-matched sibling may be used together for the transplant in cases where such cord blood cells were previously stored and found to be qualified for use as a donor for stem cell transplant.
 - 1. The HLA-matched sibling umbilical cord blood unit will be deemed qualified for use in combination with bone marrow when the matched sibling cord blood unit meets the eligibility criteria outlined in section 6 A.
 - 2. The HLA-matched sibling bone marrow will be infused first followed by HLA-matched sibling cord blood cells. The attending physician will determine the appropriate timing of infusion of the HLA-matched cord blood unit following completion of the HLA-matched sibling bone marrow graft. **However, infusion of the HLA-matched sibling cord blood unit will not begin until any acute toxicities from the bone marrow infusion have been controlled. In addition, the attending physician or Principal investigator may determine that infusion of the HLA-matched sibling cord blood**

is not clinically feasible or safe depending on the clinical circumstances and therefore may decide to NOT infuse the HLA-matched sibling cord blood.

The HLA-matched sibling cord blood unit must undergo rigorous donor screening and testing as well as evaluation for infectious disease markers as is required to release an unrelated donor cord blood unit for clinical use. If the related donor cord blood unit was processed and stored by a FACT accredited cord blood bank, then as standard practice, the documents verifying donor eligibility are available for review prior to shipment of the unit and will accompany the unit. If the cord blood unit was processed and stored by a bank that is NOT FACT accredited, documents regarding verification of HLA typing, cell count (including total nucleated cell count and CD34 if available), pre-cryopreservation viability, and infectious disease testing will be requested and reviewed prior to release of this cord blood unit for clinical use.

3. Procedures for infusion of the HLA-matched sibling bone marrow and HLA-matched sibling cord blood cells will follow institutional standard practice guidelines for each cell product.
4. Procedures for requesting, receiving and characterizing the cord blood unit for infusion will be according to institutional practice.
5. Pre-infusion hydration should be performed per institutional guidelines.
6. Conditioning and GVHD prophylaxis will be per regimen A.
7. Patients receiving HLA-matched sibling bone marrow and HLA-matched sibling cord blood products may have infusions that go over 2 days. Day 0 will be considered the day the 2nd product finishes and administration of methotrexate will be adjusted accordingly.
8. For FHCRC patients, the cord blood unit should be thawed and infused per FHCRC standard practice guidelines. Cord blood products should be infused without delay as soon as the product arrives on the unit. Outside centers should follow institutional standard practice guidelines.
9. The cord blood infusion should take no longer than 30 minutes. Pre-medications (if any) prior to cord blood infusion will be at the discretion of the attending. Under no circumstances is the cord blood to be irradiated. No medications or fluids should be given piggyback through the catheter lumen that is being used for cord blood infusion.
10. The product is infused via IV drip directly into the central line according to standard practice with gravity filtered tubing.
11. Vital signs should be monitored before beginning the bone marrow and cord blood infusion and periodically during administration. Notify the attending physician, fellow, PA or NP immediately if the patient exhibits signs or symptoms of a reaction.
12. Benadryl, epinephrine, and hydrocortisone should be available at the bedside for emergency use if necessary.
13. Oxygen with nasal prongs for standby use should be present in the room.

11. IMMUNOSUPPRESSION:

Regimen A: Bone Marrow or PBSC or recipients of HLA-matched sibling bone marrow combined with HLA-matched sibling cord blood

All patients who receive bone marrow or peripheral blood stem cells will receive 2 agents for GVHD prophylaxis as follows:

A. Tacrolimus

1. Tacrolimus should be initiated per Standard Practice Guidelines as an IV continuous infusion on day -1 at a dose of 0.03 mg/kg/day. Dosing should be based on adjusted body weight. If actual weight is less than adjusted body weight, dosing should be based on actual weight. The same lumen of the central catheter should be used for all tacrolimus infusions. Conversion to the oral formulation (IV:PO ratio 1:4) should be made when oral feeding is established. Oral tacrolimus is available in 0.5, 1 and 5 mg capsules and as a compounded suspension of 1 mg/mL. Oral tacrolimus should be given in two divided daily doses every 12 hours. If the patient vomits within one hour of taking the medication, repeat the dose. If vomiting persists, the medication should be given intravenously at the appropriate dose (PO:IV ratio 4:1). Beverages containing the enzyme bergamottin (grapefruit juice, Sunny Delight, Fresca and Squirt) should be avoided. If possible, oral tacrolimus should be taken on an empty stomach at a consistent time each day.
2. In the absence of GVHD, we recommend that the tacrolimus be tapered starting on day +50. In the absence of GVHD, the dose should be tapered by 5% each week for liquid and 20% each month for capsules. In the presence of GVHD, or if the patient is receiving corticosteroids or other therapy for GVHD, tacrolimus should not be tapered at day +50, and dosing should be maintained to target therapeutic levels. Long-term administration of tacrolimus will be per the recommendations of the Long-term Follow-up Department (LTFU).
3. *Tacrolimus levels:* Tacrolimus levels should be maintained in the range of 5-15 ng/ml. In patients who are also taking sirolimus, it is generally recommended that tacrolimus trough levels not exceed 10ng/ml. Tacrolimus levels will be performed weekly starting on day +2 through day +50 per Standard Practice Guidelines, see Calcineurin Inhibitor Therapy (Cyclosporine, Tacrolimus) section. To avoid contamination, all levels should be drawn from the central catheter port opposite the lumen used to infuse tacrolimus. If a tacrolimus taper is initiated at day +50, and the patient has adequate oral fluid intake and stable volume status, checking of blood levels may generally be discontinued once tacrolimus has been reduced by 25%. If a tacrolimus taper is not initiated, levels should be performed weekly through day +100. Tacrolimus levels should be performed more frequently **1)** when the medication is converted from oral to IV or IV to oral; **2)** when dose adjustments are made due to levels outside the therapeutic range; or **3)** if toxicity is suspected. Steady state levels will not be achieved for at least 72 hours after any change in dosing, so levels obtained earlier than this may not reflect an accurate steady state concentration.

4. Tacrolimus Toxicities:

| Common, No Specific Therapy | Common, Intervention Usual | Uncommon, May Require Intervention | Uncommon or Serious, Intervention Usual |
|--|--|---|---|
| 
 • Hypertension (controlled) • Tremor (mild) • Hyperlipidemia | 
 • Hypertension (poorly controlled) • Tremor (severe) • Hyperkalemia • Hypomagnesemia • Elevated Creatinine • Elevated BUN | 
 • Anorexia, nausea, vomiting • Diarrhea • Anemia • Back pain • Rash, pruritis • Atelectasis • Insomnia • Asthenia • Hyperglycemia • Hyperbilirubinemia • Elevated Transaminases | 
 • Pleural effusion • Coma, delirium • Hemolytic Uremic Syndrome • Dysarthria • Seizures • Hallucinations |

B. Methotrexate

1. Administration:

- a. In adults and children > 10 kg, methotrexate should be administered as an IV push at a dose of 15 mg/m² on day +1 after transplant and at 10 mg/m² on days +3, +6 and +11. Calculation of m² will be per Standard Practice Guidelines.
- b. Infants who weigh \leq 10 kg should have methotrexate dosed on a per kilogram (actual weight) basis rather than per meter squared. Therefore, the methotrexate dose is 0.5 mg/kg on Day + 1 and 0.33 mg/kg on Days +3, +6 and +11.
- c. The first dose of methotrexate should be given approximately 24 hours after completion of the initial stem cell infusion, but no sooner than 24 hours later.

2. Toxicities: In this setting, mucositis is the primary toxicity related to methotrexate. In the setting of renal or hepatic dysfunction, where there is impaired clearance of the medication, methotrexate may contribute to delayed neutrophil engraftment. Methotrexate may cause an elevation in serum transaminase.

3. Dose adjustments - Every attempt should be made to administer methotrexate as prescribed, as dose reduction or omission may increase the risk of acute GVHD. Patients at greatest risk for methotrexate -related toxicities are those with either decreased renal function or significant fluid collection (i.e. ascites, pleural effusions, etc.), where methotrexate can accumulate and, thus, delay clearance. Renal dysfunction or third space fluid accumulation are not strict contraindications to the administration of methotrexate, although dose reduction (75–50%) and rescue with leucovorin (citrovorum factor) should be considered. Similarly, while one may want to discontinue methotrexate in patients who require intubation because of severe mucositis, generally mucositis should not be a contraindication for the use of methotrexate.

4. Methotrexate levels should be monitored in patients at risk for the development of toxicity. Acceptable methotrexate levels at 24 hours or later after the administration of

methotrexate are $<0.04 \times 10^{-6}$ molar (see **Figure 3**). If toxic levels are present, leucovorin should be given per our **Standard Practice Guidelines**. The standard dose of leucovorin is 10 mg/m² IV every 6 hours.

[figure not shown]

Figure 3. Methotrexate (MTX) plasma levels and leucovorin (citrovorum) “rescue”.

Regimen B: Unrelated Umbilical Cord Blood:

All recipients of unrelated umbilical cord blood will receive prophylaxis for GVHD with 2 drugs as follows:

A. Cyclosporine A

1. Patients will receive cyclosporine A (CSA) therapy beginning on Day -3 maintaining a trough level between 200 and 400 ng/mL by HPLC analysis (250 and 500 ng/ml by immunoassay). For adults the initial dose will be 2.5 mg/kg IV over 1 hour every 12 hours. For children < 40 kg the initial dose will be 2.5 mg/kg IV over 1 hour every 8 hours. The initial dose will be based on adjusted body weight.
2. Dose adjustments will be made on the basis of toxicity and low CSA levels with trough level of <200 mg/L (HPLC). Once the patient can tolerate oral medications, CSA will be converted to an oral form. CSA dosing will be monitored and altered as clinically appropriate.
3. Patients will receive CSA until Day +100. If there is no evidence of GVHD, the dose will then be tapered 10% per week starting on Day +101 and discontinued no sooner than 6 months post-transplant.
4. Drugs that may affect CSP levels are:

| Decrease CSP levels | Increase CSP levels | |
|--|---------------------|----------------|
| Phenytoin | Erythromycin | Caspofungin |
| Phenobarbital | Ketoconazole | Azithromycin |
| Carbamazepine | Acetazolamide | Diltiazem |
| Primidone | Fluconazole* | Clarithromycin |
| Rifampicin | Colchicine | Verapamil |
| Nafcillin | Itraconazole* | Doxycycline |
| Octreotide | Fluoroquinolones | Nicardipine |
| Sulfonamides | Voriconazole | Nifedipine |
| Trimethoprim | Imipenem | Alcohol |
| Metoclopramide | | |
| *Discontinuation of fluconazole or itraconazole may lower CSP levels, and if used for antifungal prophylaxis, then changes in these drugs should be avoided during the first 2 months post-transplant. | | |

B. Mycophenolate mofetil (MMF)

1. MMF will be administered at 15 mg/kg every 8 hours with a maximum of 1 gram/dose beginning the evening of day 0 (i.e. first dose to follow 4-6 hours after UCBT). The dose will be based on adjusted body weight.
2. MMF will be given every 8 hrs daily until day 40 post-transplant and then in the absence of GVHD, tapered by 12%/week with MMF discontinued after day + 96.
3. Markedly low (<40%) donor T cell chimerism after UCBT may indicate impending graft rejection. MMF should be continued at full dose or, if MMF taper has been initiated, reinstitution of full dose MMF should occur. If MMF has been discontinued, MMF should be reinitiated at full dose.

